5.6 CLINICAL VISITS AND PROCEDURES

Demographics

Demographic information (date of birth, gender, race/ethnicity) will be recorded at Baseline visit.

Medical History

Relevant medical history, including history of current disease and information regarding underlying diseases will be recorded at Baseline visit.

Vital Signs

Weight, height, blood pressure and waist circumference will be collected and body mass index calculated at initial baseline visit and study completion visit.

Clinical Laboratory Measurements

Blood will be obtained by venipuncture at the UCSF Clinical Research Services site at Parnassus at baseline and study completion visits. We will obtain 4 tubes of blood (serum and plasma and separated into aliquots. One aliquot of serum will be sent to Quest Diagnostics for determination of fasting glucose, lipid Apo A1- and ApoB, s and A1c measurements. An aliquot of plasma will be sent to the West Coast Metabolomics Center at the University of California, Davis, for determination of targeted amino acid metabolomics analysis. The remaining aliquots will be frozen at -80C for future research. See Table 1 for Study procedures at each visit.

Telephone Screening

Individuals who respond to recruitment notices will be provided with a general overview of the program and will complete a brief telephone survey to determine initial eligibility (age, prediabetes diagnosis) before being invited to the screening visit.

Baseline clinic visit

At the baseline visit, the study will be explained in detail, and informed consent will be obtained. Candidates will be told that this is a trial of walnut supplementation to improve dietary quality in overweight or obese individuals with prediabetes.

The research coordinator will perform measurement of height using a stadiometer and weight using a digital scale. Those with a BMI $\geq 25 \text{ kg/m}^2$ ($\geq 23 \text{ kg/m}^2$ if of Asian or South Asian ethnicity) will be eligible. The research coordinator will then perform a capillary blood glucose measurement using an Accu-check Aviva Connect blood glucose meter and Accu-Check test strips. A capillary blood glucose value of 100mg/dL and higher will be considered eligible for participation in the study.

Eligible participants will be randomized into “Walnuts Now” and “Walnuts Later” groups. They will complete questionnaires about demographic and medical history, health-related behaviors including satiety, and medications. A research coordinator will measure height, weight, waist circumference and blood pressure. The participants will undergo venipuncture and fasting blood draw. One tube of serum will be sent to Quest for measurement of fasting glucose, hemoglobin A1c and serum lipids as well as apolipoprotein A2 and B. One tube will be aliquotted into 1mL cryogenic tubes. One aliquot of plasma will be shipped to the West Coast Metabolomics Center at the University of California, Davis for amino acid and acylcarnitine analyses. The remaining serum and plasma aliquots will be de-identified, frozen at -80C and stored for future analyses.

All participants will receive handouts regarding a healthy diet to prevent diabetes.

The research coordinator will dispense 12-week supply of individually-wrapped, raw walnuts to “Walnuts Now” group.

6-week Telephone Follow-up

The research coordinator will reach out to study participants by phone at 6 weeks to remind intervention participants of daily walnut intervention, give a reminder of healthy eating habits to all participants, and schedule Study Conclusion visit.

Study Completion Visit

At study completion, all participants will be invited back for a study completion visit. At this visit, a research assistant will record height, weight, blood pressure and waist circumference. The participants will undergo venipuncture and fasting blood draw. One tube of serum will be sent to Quest for measurement of fasting glucose, hemoglobin A1c and serum lipids as well as apolipoprotein A2 and B. One tube will be aliquotted into 1mL cryogenic tubes. One aliquot of plasma will be shipped to the West Coast Metabolomics Center at the University of California, Davis for amino acid and acylcarnitine analyses. The remaining serum and plasma aliquots will be de-identified, frozen at -80C and stored for future analyses.

All participants will receive handouts regarding a healthy diet to prevent diabetes.

The research coordinator will dispense 12-week supply of individually-wrapped, raw walnuts to “Walnuts Later” group.

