5.2 Study Overview

This is a single-center, unblinded, randomized-controlled trial. 40 study subjects are planned. Each subject will consume 28g of individually wrapped raw, unsalted walnuts daily for a total of 12 weeks. Participants will be assigned to the treatments in random order. Evaluations will be taken at baseline and at end-of-study.

Screening data will be reviewed to determine subject eligibility. Subjects who meet all inclusion criteria and none of the exclusion criteria will be entered into the study.

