5.5 Supply and Dispensing of Intervention Food at the Study Site

A 12-week supply of individually-wrapped walnut packets will be given to intervention-group participants at enrollment in the study. Those randomized to the control group will receive a 12-week supply of walnuts at the final study visit.

The California Walnut Commission will ship the walnuts to the study site in boxes of 200 individually-wrapped samples in 2 installments – in June 2017 and August 2017. Walnuts will be shipped and kept in cold storage according to the attached protocol. If a participant has concerns about the quality of the walnuts, they will contact the study coordinator who will initiate the following protocol from the California Walnut Commission:

- 1) Have participant return package and remaining product
- 2) Check walnut batch (lot number, date, size of package) where package obtained, if possible
- 3) Contact [name] RD, directly and immediately.

[name] RDN, FAND

[contact]

[contact]

Dosage/Dosage Regimen

We will test a dose of 28g of walnuts daily for the experimental group participants. The walnuts should ideally be consumed without added salt or roasting. This whole-food supplement will be given in conjunction with dietary advice to replace consumption of added sugars and refined carbohydrates

Dispensing

The study coordinator will provide a 12 week supply of walnuts to the intervention participants at the enrollment visit. The study coordinator will provide an equivalent supply of walnuts to the control participants at the study conclusion visit.

Administration Instructions

The participants will consume one 28-gram packet of walnuts daily. This may be consumed at one sitting or throughout the day. Walnuts should replace added sugars or products with refined carbohydrates.

Supply of Food Supplement at the Site

The individually wrapped walnut packages will be delivered from the California Walnut Commission in 2 installments. The first in early June and the second in early August.

Storage

The individually wrapped walnuts will be stored in cold storage until they are given to the participants.

Measures of Treatment Compliance

Subjects will be asked to keep a patient diary noting the day and date they consume their allocated walnut packet and any adverse events. They will be asked to bring their patient diary to each study visit.

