5.7 Measures Collected at Each Visit

Table 1: Measurements at each Study Visit				
Visit	Telephone Screening (Week 0)	Baseline visit (Week 1)	Telephone Mid-Point (6 weeks)	Study completion (12 weeks)
Informed Consent	Verbal informed Consent	Written informed consent		
Questionnaires	Initial eligibility screen	Demographic questionnaire Block food frequency Self-efficacy		Acceptability Palatability Adherence Block food frequency Self-efficacy
Clinical measurements		Height Weight Waist circumference Blood pressure Capillary blood glucose		Height Weight Waist circumference Blood pressure
Laboratory analyses		Fasting glucose HbA1c Lipids BCAA, AAA, acylcarnitines		Fasting glucose HbA1c Lipids BCAA, AAA, acylcarnitines
Counseling		Dietary and exercise counseling for both intervention and control arms	Check-in for diet and exercise changes Adherence to walnut supplement for "Walnuts Now" group.	
Dispensing of Study Intervention		"Walnuts Now" Intervention Group receives a 12-week supply of walnuts		"Walnuts Later" Control Group receives a 12-week supply of walnuts

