Dietary Quality: A Block food frequency questionnaire will be administered to participants at enrollment and completion of the study period. This questionnaire will use patient recall to gather frequency and serving size data for all participants. We will use the responses in this questionnaire to determine consumption of foods grouped based on likeness and culinary usage. These categories will then be transformed into 2 dietary scores: the Healthy Eating Index-2010 score, based on the Dietary Guidelines for Americans, which is a continuous score ranging from 0-100, with a score of 100 representing the optimal diet. We will also calculate the Mediterranean Diet Score, with possible values from 0-55, with 55 representing the diet most congruent with the Mediterranean diet.

BCAA, AAA and acylcarnitines: Targeted amino acid and acylcarnitine levels will be measured at baseline and at 12 weeks, post-intervention using triple quadrupole (MS/MS) and gas chromatography instruments. We will collaborate with the West Coast Metabolomic Center on the metabolomics analyses and interpretation.

Statistical Analysis: This is designed as a parallel group controlled trial, randomized on dichotomized age (<50 or \geq years) and sex (female or male). We will use Fisher's exact test and Student's t-test to compare mean baseline demographic and clinical

characteristics between the intervention and control groups. Using information from the Block food frequency questionnaire, we will construct a continuous dietary quality score using the Healthy Eating Index 2010 and Mediterranean Diet Score criteria. We will use analysis of covariance to compute the adjusted mean for our outcome variables of fasting glucose, HbA1c, HDL, LDL, total cholesterol and amino acid levels. In analysis of covariance, the baseline value of outcome variables will be used as a covariate for the computation of adjusted means between the two groups after intervention.

Expected Results: We believe that walnut supplementation will be acceptable at a dose of 28g daily. We expect to be able to recruit 40 participants within 3 months, and retain >75% for the full 12 weeks of the intervention. We expect to see a trend towards significant change in the BCAA and AAA measurements and some improvements of fasting glucose and HbA1c in the “Walnut” group compared to the “Usual care” group.

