Capillary blood glucose measurement: The baseline visit will require fingerstick collection of one drop of blood for determination of eligibility. This may result in pain or discomfort. We do not anticipate other problems from this procedure in healthy adults.

Phlebotomy and venipuncture: The baseline visit and study conclusion visit 3-month visit will require approximately 35-45 ml of venous blood collection. We do not anticipate any problems with anemia with a total of 45 ml of blood collection in our study of healthy volunteers. Venipuncture may result in a hematoma, which can be painful but carries no significant risks. Infections rarely occur from such brief interventions.

Walnut supplementation: There is minimal risk associated with participation in the walnut intervention. There is the possibility of an allergic reaction to the walnut supplement. We will actively exclude any participants with a known tree nut or peanut allergy from enrollment in the study. There is the small possibility that an as-yet, unknown, allergy to walnuts will occur during the course of the study. In the event of signs or symptoms of allergy, the walnut intervention will be discontinued. Participants will be educated on signs and symptoms of a walnut allergy at the baseline visit. In order to protect the integrity and freshness of the walnuts, they will be kept in cold storage at the study site, and participants will be instructed to keep them in cold storage in their private homes before use.

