6.2 Adequacy of Protection Against Risks

6.2.a Recruitment and Informed Consent: Recruitment will be accomplished primarily through a medical records query, and through flyers at Parnassus and Mount Zion UCSF campuses. At the beginning of the baseline visit, a member of the research staff will review the consent form in detail with the patient and answer all questions before inviting the patient to sign the consent form. A photocopy of the signed consent form with the Experimental Subjects' Bill of Rights is given to the patient. The protocols are reviewed by the Institutional Committee on Human Research, University of California, San Francisco and University of California, San Diego. All subjects will be reimbursed for the time and possible inconvenience associated with participation in the studies.

6.2.b Protection Against Risk: The specific measures to minimize each risk are described in the relevant sections above, as well as the Data Safety and Monitoring Plan that is outlined in a subsequent section. In addition, there will be continuous safety surveillance with emphasis on the potential side effects of each procedure, as detailed above. Participation in the study will be discontinued if the subject fails to adhere to the study requirements in a way that may cause harm to him or herself or seriously interfere with the validity of the study results; or the investigator determines that further participation would be detrimental to the subject's health or well being.

Subjects who are injured as a result of being in this study will have treatment available.

The costs of such treatments may be covered by the University of California depending on a number of factors.

Participation in research may involve a loss of privacy. Research records will be kept confidential to the extent permitted by law. Subjects will be identified by a code, and personal information from records will not be released without written permission. Subjects will not be personally identified in any publication about this study.

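### Minor, cheap improvement: no adverse-event question is specified between baseline and week 12, so the month 2 safety review has no solicited on-treatment data, and there is no step to obtain events or reasons from people who miss week 12

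*Combined protocol and SAP*

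**What the plan says.** **How events are recorded.** Section 5.5 (Measures of Treatment Compliance) states: "Subjects will be asked to keep a patient diary noting the day and date they consume their allocated walnut packet and any adverse events". On its return: "They will be asked to bring their patient diary to each study visit".

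**When participants are seen.** Section 5.2: "Evaluations will be taken at baseline and at end-of-study". Table 1 in section 5.7 agrees, with a baseline visit, a telephone mid-point at 6 weeks and a completion visit at 12 weeks.

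**What the 6-week call contains.** Section 5.6: "The research coordinator will reach out to study participants by phone at 6 weeks to remind intervention participants of daily walnut intervention". The sentence goes on to a healthy-eating reminder and scheduling of the last visit. Table 1 adds a check on diet and exercise and on walnut adherence. Neither has an adverse-event item. The week-12 text and the week-12 column of Table 1 list none either.

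**What is reviewed, and when.** Section 6.5.c assigns adverse-event rates to the PI monthly, and 6.5.d has the PI review progress and safety monthly. The annual report in 6.5.d must address whether adverse-event rates fit pre-study assumptions and why people dropped out.

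**Other safety provisions.** Section 6.5.b gives participants a number to call between visits and a private opportunity to raise complaints. Section 6.2.b promises "continuous safety surveillance with emphasis on the potential side effects of each procedure". Known nut allergy is an exclusion, allergy signs are taught at baseline, serious events are reported, and section 6.1.c adds: "In the event of signs or symptoms of allergy, the walnut intervention will be discontinued".

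**The concern.** The review schedule and the data flow do not match. Safety is reviewed every month, but the one record that asks participants about adverse events first comes back at week 12. Until then, followed as written, the PI sees only what a participant chooses to phone in or what comes up at an unscheduled moment.

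The expected risk named in section 6.5.b is mild gastrointestinal upset. That is the kind of event people may tolerate, or quietly stop eating the walnuts over, without telephoning. It also bears on acceptability and adherence, which are Aim 1.

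The second gap lasts beyond the early reviews. A participant who misses week 12 does not hand in the diary at a visit, and the plan describes no contact to recover its entries or the reason for stopping. These are the people for whom tolerability may matter most, and the annual report has to account for them.

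**Working it through.** The documents give no figure to reproduce here. The check is of the calendar, followed by a count of how much data each review would have.

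**Step 1: calendar, free of any accrual assumption.** Count from the first enrolment. The month 2 review falls near day 61 (2 × 30.44 days). The first on-treatment diary returns at day 84 (12 weeks), or day 77 if baseline is taken as week 1, as Table 1 labels it. Both are later than day 61. Diaries in hand at the month 1 and month 2 reviews are therefore 0 and 0 for any accrual pattern. The first 6-week call falls at day 42, which is after month 1 and before month 2.

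**Step 2: inputs for the counts.**
- 20 walnut participants (section 5.4).
- 3-month recruitment (section 5.7, Expected Results), taken as 13 weeks.
- 12 weeks of walnuts each.
- Lag L from contact to review of 0, 1 or 2 weeks. Section 6.5.c sets a data-entry goal under 1 week and an acceptable limit under 2 weeks.
- Assumptions not in the documents: even accrual, every call made at exactly 6 weeks, and everyone attending week 12. The counts of calls and of diaries are both upper values for that reason.

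**Step 3: formulas.** With a review at t weeks (4.33, 8.67, 13, 17.33), floor 0 and cap 20:
- Diaries back = 20 × (t − 12 − L) / 13
- Participants queried by phone = 20 × (t − 6 − L) / 13

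Example, month 2, L = 0: 20 × (8.67 − 6) / 13 = 4.10.

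| Walnut participants with solicited data | Month 1 | Month 2 | Month 3 | Month 4 |
|---|---|---|---|---|
| As written, L = 0 | 0 | 0 | 1.54 | 8.21 |
| With query, L = 0 | 0 | 4.10 | 10.77 | 17.44 |
| As written, L = 1 | 0 | 0 | 0 | 6.67 |
| With query, L = 1 | 0 | 2.56 | 9.23 | 15.90 |
| As written, L = 2 | 0 | 0 | 0 | 5.13 |
| With query, L = 2 | 0 | 1.03 | 7.69 | 14.36 |

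If starts are random rather than even, the binomial 5th to 95th percentiles at L = 0 are 1 to 7 queried at month 2, 7 to 14 queried at month 3, and 0 to 4 diaries at month 3.

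**Step 4: exposure covered.** Walnut person-weeks elapsed at months 2 and 3 are 57.8 and 129.2. A call covers 6 weeks, and a returned diary covers 12.
- Month 2, as written: 0%. With the query: 6 × 4.10 / 57.8 = 43% at L = 0, 6 × 2.56 / 57.8 = 27% at L = 1, and 6 × 1.03 / 57.8 = 11% at L = 2.
- Month 3, L = 0, as written: 12 × 1.54 / 129.2 = 14%. With the query: (6 × 10.77 + 6 × 1.54) / 129.2 = 57%.

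**Step 5: non-attenders.** The plan states: "We expect to be able to recruit 40 participants within 3 months, and retain >75% for the full 12 weeks of the intervention". Trial-wide, 40 × 0.25 = 10, so fewer than 10 people would miss week 12 if that expectation holds.

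**The case against.** The strongest reply is that this argues from silence in lists that are visibly incomplete. Table 1 has no adverse-event row at any visit, and it omits medical history and the diary, both planned elsewhere. The 6-week text omits the adherence check that Table 1 includes. A coordinator checking adherence by phone could well ask for the diary, which holds both packets eaten and adverse events. This stands in part. The call script is not in the documents, so a reader might infer that nobody would ask about adverse events at 6 weeks, and the documents do not support that. They support only that no such question is specified. The contact number depends on the participant, and the private discussion and general surveillance statement set no time or form, so none of them is a scheduled point for asking.

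Second, the consequences are limited. Acceptability and palatability are assessed at the end of the intervention, and adherence from the diary and the completion questionnaire, so for completers Aim 1 loses nothing from diary return at week 12. That stands. The monthly item on adverse-event rates carries a parenthetical reference to injuries, which may not include mild gastrointestinal upset. However, section 6.5.d promises a general monthly safety review as well. No stopping rule depends on mild-event rates.

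Third, a reader might infer that serious harm would go unnoticed. The allergy exclusion, the teaching of allergy signs, stopping walnuts on allergy symptoms, and serious-event reporting all argue against that.

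Fourth, a 6-week query does nothing for month 1, and the month 2 gain shrinks quickly with lag. Both points are correct and limit the claim.

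**Conclusion.** The point holds as a minor, low-cost improvement. As written, the month 2 review has no solicited on-treatment adverse-event data, whatever the accrual pattern, and nothing is described for recovering diary entries or reasons from people who miss week 12.

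The gain at month 2 is modest: between 1.0 and 4.1 of 20 walnut participants, or 11% to 43% of elapsed exposure, depending on lag. It is larger by month 3, at about 11 participants against 1.5 with no lag. These counts rest on even accrual, punctual calls and full attendance. They measure people and exposure covered. The documents give no adverse-event rate, so no number of missed events can be stated.

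**What to change.** - In section 5.6 and Table 1, add a brief fixed adverse-event query for both arms at the 6-week call and again at the week-12 visit: gastrointestinal symptoms, suspected allergic symptoms, any other event.
- Have diary entries read out at the call where a diary is kept. The diary is described in terms of the allocated walnut packet, so usual-care participants may not have one, and the query should not depend on it.
- Record the answers on a short form and pass them to the next monthly PI review (section 6.5).
- For anyone who misses week 12, make one phone contact to obtain any diary adverse-event entries and the reason for stopping.

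The cost is a few minutes on contacts already scheduled, one short form, some extra mild-event data for the PI to read, and fewer than 10 additional calls if retention exceeds 75%. No new visit, staff or committee is needed. Solicited data at month 1 would need an earlier contact, for example at 2 to 4 weeks, or remote return of the diary. Given the minimal risk, that is optional.

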5.7 Measures Collected at Each Visit

Table 1: Measurements at each Study Visit				
Visit	Telephone Screening (Week 0)	Baseline visit (Week 1)	Telephone Mid-Point (6 weeks)	Study completion (12 weeks)
Informed Consent	Verbal informed Consent	Written informed consent		
Questionnaires	Initial eligibility screen	Demographic questionnaire Block food frequency Self-efficacy		Acceptability Palatability Adherence Block food frequency Self-efficacy
Clinical measurements		Height Weight Waist circumference Blood pressure Capillary blood glucose		Height Weight Waist circumference Blood pressure
Laboratory analyses		Fasting glucose HbA1c Lipids BCAA, AAA, acylcarnitines		Fasting glucose HbA1c Lipids BCAA, AAA, acylcarnitines
Counseling		Dietary and exercise counseling for both intervention and control arms	Check-in for diet and exercise changes Adherence to walnut supplement for "Walnuts Now" group.	
Dispensing of Study Intervention		"Walnuts Now" Intervention Group receives a 12-week supply of walnuts		"Walnuts Later" Control Group receives a 12-week supply of walnuts

